9.1.3. Solicited adverse events

Solicited local and general AEs occurring during a 7-day follow-up period after each vaccination (*i.e.* the day of vaccination and the 6 subsequent days), as well as unsolicited AEs occurring during a 30-day follow-up period after each vaccination (*i.e.* the day of vaccination and the 29 subsequent days), will be reported via paper Diary Cards for vaccine reactogenicity and recorded via the appropriate section of the eCRF.

9.1.3.1. Solicited local (injection-site) adverse events

The following local (injection-site) AEs will be solicited:

Table 18 Solicited local adverse events

Pain at injection site
Redness at injection site
Swelling at injection site

9.1.3.2. Solicited general adverse events

The following general AEs will be solicited:

Table 19 Solicited general adverse events

Fatigue
Fever
Gastrointestinal symptoms [†]
Headache

[†] Gastrointestinal symptoms include nausea, vomiting, diarrhoea and/or abdominal pain.

Note: temperature will be recorded in the evening. Should additional temperature measurements be performed at other times of day, the highest temperature will be recorded in the eCRF.

9.1.4. Clinical laboratory parameters and other abnormal assessments qualifying as adverse events or serious adverse events

In absence of diagnosis, abnormal laboratory findings (*e.g.* clinical chemistry, haematology, urinalysis) or other abnormal assessments that are judged by the investigator to be clinically significant will be recorded as AE or SAE if they meet the definition of an AE or SAE (refer to Sections 9.1.1 and 9.1.2). Clinically significant abnormal laboratory findings or other abnormal assessments that are present at baseline and significantly worsen following the start of the study will also be reported as AEs or SAEs. However, clinically significant abnormal laboratory findings or other abnormal assessments that are associated with the disease being studied, unless judged by the investigator as more severe than expected for the subject's condition, or that are present or detected at the start of the study and do not worsen, will not be reported as AEs or SAEs.

The investigator will exercise his or her medical and scientific judgement in deciding whether an abnormal laboratory finding or other abnormal assessment is clinically significant.

9.1.5. Adverse events of specific interest (potential immune-mediated diseases)

PIMDs are a subset of AEs that include autoimmune diseases and other inflammatory and/or neurologic disorders of interest which may or may not have an autoimmune

aetiology. AEs that need to be recorded and reported as pIMDs include those listed in [Table 20](#).

However, the investigator will exercise his/her medical and scientific judgement in deciding whether other diseases have an autoimmune origin (*i.e.* pathophysiology involving systemic or organ-specific pathogenic autoantibodies) and should also be recorded as a pIMD.

Table 20 List of potential immune-mediated diseases

Neuroinflammatory disorders	Musculoskeletal disorders	Skin disorders

 • Cranial nerve disorders, including paralyses/paresis (e.g. Bell's palsy) • Optic neuritis • Multiple sclerosis • Transverse myelitis • Guillain-Barré syndrome, including Miller Fisher syndrome and other variants • Acute disseminated encephalomyelitis, including site specific variants: e.g. non-infectious encephalitis, encephalomyelitis, myelitis, myeloradiculoneuritis • Myasthenia gravis, including Lambert-Eaton myasthenic syndrome • Immune-mediated peripheral neuropathies and plexopathies, (including chronic inflammatory demyelinating polyneuropathy, multifocal motor neuropathy and polyneuropathies associated with monoclonal gammopathy). • Narcolepsy 	
 • Systemic lupus erythematosus • Scleroderma, including diffuse systemic form and CREST syndrome • Systemic sclerosis • Dermatomyositis • Polymyositis • Antisynthetase syndrome • Rheumatoid arthritis, • Juvenile chronic arthritis, (including Still's disease) • Polymyalgia rheumatica • Spondyloarthritis, including ankylosing spondylitis, reactive arthritis (Reiter's Syndrome) and undifferentiated spondyloarthritis • Psoriatic arthropathy • Relapsing polychondritis • Mixed connective tissue disorder 	
 • Psoriasis • Vitiligo • Erythema nodosum • Autoimmune bullous skin diseases (including pemphigus, pemphigoid and dermatitis herpetiformis) • Cutaneous lupus erythematosus • Alopecia areata • Lichen planus • Sweet's syndrome • Morphea
Liver disorders	Gastrointestinal disorders	Metabolic diseases

 • Autoimmune hepatitis • Primary biliary cirrhosis • Primary sclerosing cholangitis • Autoimmune cholangitis 	
 • Crohn's disease • Ulcerative colitis • Ulcerative proctitis • Celiac disease 	
 • Autoimmune thyroiditis (including Hashimoto thyroiditis) • Grave's or Basedow's disease • Diabetes mellitus type I • Addison's disease
Vasculitides		Others

 • Large vessels vasculitis including: giant cell arteritis such as Takayasu's arteritis and temporal arteritis. • Medium sized and/or small vessels vasculitis including: polyarteritis nodosa, Kawasaki's disease, microscopic polyangiitis, Wegener's granulomatosis, Churg-Strauss syndrome (allergic granulomatous angiitis), Buerger's disease (thromboangiitis obliterans), necrotizing vasculitis and anti-neutrophil cytoplasmic antibody (ANCA) positive vasculitis (type unspecified), Henoch-Schonlein purpura, Behcet's syndrome, leukocytoclastic vasculitis. 	
 • Autoimmune hemolytic anemia • Autoimmune thrombocytopenia • Antiphospholipid syndrome • Pernicious anemia • Autoimmune glomerulonephritis (including IgA nephropathy, glomerulonephritis rapidly progressive, membranous glomerulonephritis, membranoproliferative glomerulonephritis, and mesangiproliferative glomerulonephritis) • Uveitis • Autoimmune myocarditis cardiomyopathy • Sarcoidosis • Stevens-Johnson syndrome • Sjögren's syndrome • Idiopathic pulmonary fibrosis • Goodpasture syndrome • Raynaud's phenomenon 	

When there is enough evidence to make any of the above diagnoses, the AE must be reported as a pIMD. Symptoms, signs or conditions which might (or might not) represent the above diagnoses, should be recorded and reported as AEs but not as pIMDs until the

final or definitive diagnosis has been determined, and alternative diagnoses have been eliminated or shown to be less likely.

In order to facilitate the documentation of pIMDs in the eCRF, a pIMD standard questionnaire and a list of preferred terms (PTs) and PT codes corresponding to the above diagnoses will be available to investigators at study start.

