1.3.1. Risk Assessment

Important Potential/Identified Risk	Data/Rationale for Risk	Mitigation Strategy
NTHi investigational vaccine		
Theoretical risk of acquiring a vaccine-induced autoimmune disease after vaccination	No confirmed signals related to this potential risk have been identified during the preclinical and clinical programs so far (data from two studies using NTHi vaccines: NTHi-002 (non-adjuvanted formulations) and NTHi-003 (adjuvanted and non-adjuvanted formulations)).	Close monitoring of potential immune-mediated diseases in clinical development programs using adjuvants systems. The potential risk of events of possible autoimmune aetiology to occur is mentioned in the Informed Consent Form (ICF).

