9.3. Detecting and recording adverse events, serious adverse events and pregnancies

9.3.1. Time period for detecting and recording adverse events, serious adverse events and pregnancies

All AEs starting within 29 days following administration of each dose of study vaccine must be recorded into appropriate section of the eCRF, irrespective of intensity or whether or not they are considered vaccination-related.

All AEs/ SAEs leading to withdrawal from the study will be collected and recorded from the time of the first receipt of study vaccine until study conclusion.

The time period for collecting and recording pIMDs will begin at the first receipt of study vaccine and will end at study conclusion. See section [9.4](#) for instructions on reporting of pIMDs.

The time period for collecting and recording SAEs will begin at the first receipt of study vaccine and will end at study conclusion. See Section [9.4](#) for instructions on reporting of SAEs.

In addition to the above-mentioned reporting requirements for SAEs and in order to fulfil international reporting obligations, SAEs that are related to study participation (*i.e.* protocol-mandated procedures, invasive tests, a change from existing therapy) or are related to a concurrent GSK medication/vaccine will be collected and recorded from the time the subject consents to participate in the study until she/ he is discharged from the study. See Section [9.4](#) for instructions on reporting of SAEs.

The time period for collecting and recording pregnancies will begin at the first receipt of study vaccine and will end 6 months following administration of the last dose of study vaccine. See section [9.4](#) for instructions on reporting of pregnancies.

The time period for collecting and recording intercurrent medical conditions that require medical attention will begin at the first receipt of study vaccine and will end at study conclusion.

An overview of the protocol-required reporting periods for AEs, SAEs, and pregnancies is given in [Table 21](#).

Table 21 Reporting periods for adverse events, serious adverse events and pregnancies

Visit	Screening Visit*	V1	6 days	29 days	V4	6 days	29 days	6 months	Study Conclusion
Timepoint		Dose 1	post-Dose 1	post-Dose 1	Dose 2	post-Dose 2	post-Dose 2	post-Dose 2	D240 D450
Solicited local and general AEs									
Unsolicited AEs									
AEs/ SAEs leading to study withdrawal									
plMDs									
SAEs									

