9.4.6. Regulatory reporting requirements for serious adverse events

The investigator will promptly report all SAEs to GSK in accordance with the procedures detailed in Section 9.4.1. GSK Biologicals has a legal responsibility to promptly notify, as appropriate, both the local regulatory authority and other regulatory agencies about the safety of a product under clinical investigation. Prompt notification of SAEs by the investigator to the Study Contact for Reporting SAEs is essential so that legal obligations and ethical responsibilities towards the safety of other subjects are met.

Investigator safety reports are prepared according to the current GSK policy and are forwarded to investigators as necessary. An investigator safety report is prepared for a SAE(s) that is both attributable to the investigational vaccine/ product and unexpected. The purpose of the report is to fulfil specific regulatory and GCP requirements, regarding the product under investigation.

9.5. Follow-up of adverse events, serious adverse events, and pregnancies**9.5.1. Follow-up of adverse events and serious adverse events****9.5.1.1. Follow-up during the study**

After the initial AE/ SAE report, the investigator is required to proactively follow each subject and provide additional relevant information on the subject's condition to GSK Biologicals (within 24 hours for SAEs; refer to [Table 23](#)).

All AEs documented at a previous visit/ contact and designated as not recovered/ not resolved or recovering/ resolving will be reviewed at subsequent visits/ contacts until 30 days after the last vaccination.

All pIMDs (serious or non-serious) and SAEs documented at a previous visit/ contact and designated as not recovered/not resolved or recovering/ resolving will be reviewed at subsequent visits/contacts.

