9.5.1.2. Follow-up after the subject is discharged from the study

The investigator will follow subjects with pIMDs (serious or non-serious), SAEs or subjects withdrawn from the study as a result of an AE until the event has resolved,

subsided, stabilised, disappeared, or until the event is otherwise explained, or the subject is lost to follow-up.

If the investigator receives additional relevant information on a previously reported SAE, he/ she will provide this information to GSK Biologicals using a paper SAE and/ or pregnancy report as applicable.

GSK Biologicals may request that the investigator performs or arranges the conduct of additional clinical examinations/ tests and/ or evaluations to elucidate as fully as possible the nature and/ or causality of the AE or SAE. The investigator is obliged to assist. If a subject dies during participation in the study or during a recognised follow-up period, GSK Biologicals will be provided with any available post-mortem findings, including histopathology.

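### Suspected immune-mediated disease is held as an AE until diagnosed, but required AE recording and review close by about Day 90, so a non-serious case still undiagnosed at study end is not assured a record or follow-up

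*Protocol*

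**What the plan says.** Autoimmune disease is the only risk in the table of Protocol 1.3.1, and the stated mitigation is "Close monitoring of potential immune-mediated diseases in clinical development programs using adjuvants systems". Occurrence of any pIMD from first vaccination to study conclusion is a primary endpoint (11.1).

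The recording and follow-up rules are these:

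- **Suspected cases (9.1.5).** Symptoms, signs or conditions that might be a listed disease "should be recorded and reported as AEs but not as pIMDs until the" diagnosis is definitive and alternatives are ruled out or made less likely.
- **AE recording (9.3.1).** "All AEs starting within 29 days following administration of each dose of study vaccine must be recorded into appropriate section of the eCRF".
- **AE follow-up in the study (9.5.1.1).** Unresolved AEs "will be reviewed at subsequent visits/ contacts until 30 days after the last vaccination". The next sentence sets no such limit for pIMDs and SAEs.
- **pIMD collection (9.3.1).** "The time period for collecting and recording pIMDs will begin at the first receipt of study vaccine and will end at study conclusion". The 24-hour reporting clock in Table 23 starts when the diagnosis is established. SAEs and AEs leading to withdrawal are also collected to study conclusion.
- **Follow-up after discharge (9.5.1.2).** "The investigator will follow subjects with pIMDs (serious or non-serious), SAEs or subjects withdrawn from the study as a result of an AE", until resolution, stabilisation, explanation or loss to follow-up.
- **Schedules (Tables 7 and 8).** AE recording is marked as an eCRF entry at all ten visits, Visit 1 to Visit 10, and at both types of exacerbation contact.
- **Intercurrent medical conditions (7.7, 9.3.1).** Those needing medical attention are checked at each visit and recorded in the eCRF to study conclusion. Section 7.7 uses them to decide elimination from the ATP immunogenicity analyses.

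**The concern.** Section 9.1.5 sends suspected cases to the AE category, and 9.3.1 and 9.5.1.1 close that category long before the study ends. The unlimited in-study review and the post-discharge follow-up meant for immune-mediated disease apply only once a diagnosis exists. Table 21 has no row for a suspected pIMD.

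Take new joint swelling or neuropathy at Day 200, still under work-up at Day 450, not serious and not leading to withdrawal. Under 9.3.1 it need not be recorded as an AE, and under 9.1.5 it may not be recorded as a pIMD. Under 9.5.1.2 nobody is obliged to follow it to a diagnosis. If it were later diagnosed as a non-serious pIMD, 9.3.2 would not require a report, because after discharge it obliges the investigator to notify only related SAEs that come to notice.

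At stake is the trail from onset to diagnosis and causality for the one risk the protocol names. With about 70 vaccinees few events are expected, so a single untraced case could matter.

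**Working it through.** **1. The plan's own detection figure (Protocol 11.4).** With n = 70, the probability of at least one event is 1 − (1 − p)^70.

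- p = 1%: 1 − 0.99^70 = 50.5% (plan: more than 50%).
- p = 5%: 1 − 0.95^70 = 97.2% (plan: more than 97%).

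Both statements reproduce. At p = 1% the expected number of cases is 70 × 0.01 = 0.7.

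**2. Time covered by required AE recording.** Inputs are doses at Day 0 and Day 60, end at Day 450 (Protocol 3), and 30-day windows (11.1).

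- Windows: Days 0–29 and 60–89, so 2 × 30 = 60 days.
- Study: Days 0–450, so 451 days; 60/451 = 13.3%.
- Outside: Days 30–59 (30 days) and 90–450 (361 days), together 391 days; 391/451 = 86.7%.
- Longest schedule in Table 9: 75 + 45 + 390 = Day 510, so 511 days; 60/511 = 11.7%.

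These are shares of calendar time only.

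**3. What each kind of case is assured under the text of 9.1.5 to 9.5.1.2.**

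| Case | Record required | Follow-up required |
|---|---|---|
| Diagnosed as a pIMD by Day 450, any onset | pIMD, with causality | Yes, including after discharge |
| Suspected, and serious | SAE, with causality | Yes, including after discharge |
| Suspected, leading to withdrawal | AE, with causality | Yes, including after discharge |
| Suspected, non-serious, onset inside a window | AE, with causality | Only to 30 days after the last vaccination |
| Suspected, non-serious, onset outside the windows | None as an AE; an intercurrent condition if medical attention is needed | None |

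The gap is the last two rows, for subjects still undiagnosed at study conclusion.

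**4. Whether the analysis would show such a case.** Protocol 11.8 and SAP Amendment 1, Section 6.1.1, tabulate unsolicited symptoms only for the 30 days after a dose. An AE entered at Visit 9 because Table 7 asks for it would reach no planned unsolicited-AE table. Neither document plans a safety tabulation of intercurrent conditions. SAP Amendment 1, Section 6.1, mentions intercurrent morbidity only among the demographic and baseline summaries.

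**5. Sensitivity, by assumption only.** The documents give no diagnostic delay and no share of cases that would be traced. If a share c of cases with 1% true incidence were traceable, the chance of seeing at least one is 1 − (1 − 0.01c)^70: 50.5% for c = 1, 41.0% for 0.75, 29.6% for 0.5 and 16.1% for 0.25. This shows how the plan's detection figure responds to c; it does not estimate c.

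**The case against.** The strongest reply is that most routes are open.

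- A case diagnosed on any day up to Day 450 is collected whatever its onset, reported within 24 hours with causality, and followed. This stands.
- Serious cases, including important medical events short of hospitalisation (9.1.2), and AE withdrawals need no diagnosis to be collected. This stands.
- The diagnostic bar is not absolute. Section 9.1.5 asks for enough evidence, allows alternatives to be merely less likely, and leaves room for investigator judgement. This stands, and it shortens the list of affected subjects.
- Tables 7 and 8 schedule AE recording to the end of the study, and 9.3.1 states a minimum rather than a prohibition. This stands in part. The schedules contradict the 29-day limit, so sites may act differently, and late entries still fall outside the 30-day tabulation.
- A subject under work-up is receiving medical attention, so the condition enters the eCRF as intercurrent. This also stands in part. Section 9.3.3.2.2 requires causality for AEs and SAEs, not for these entries.

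A further reply concerns the endpoint. It counts diagnosed pIMDs, so a longer AE window would not by itself add to the count, and any diagnosis-based endpoint with finite follow-up misses cases diagnosed later. That is correct. What the AE rules affect is the record and follow-up of the suspected case, not the definition of the endpoint.

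**Conclusion.** The gap is real but narrow. It concerns suspected pIMDs that are non-serious, do not lead to withdrawal and remain undiagnosed at study conclusion. Those with onset outside Days 0–29 after a dose are not assured an AE record, a causality assessment, a safety tabulation or follow-up after discharge. Those with onset inside a window have a record but no required review after about Day 90. The conclusion rests on reading 9.3.1 and 9.5.1.1 as written; the conflict with Tables 7 and 8 leaves practice uncertain.

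Three stronger readings are tempting, and the documents support none of them:

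- **Late-onset cases are lost.** They are collected if diagnosed by Day 450, serious or a cause of withdrawal, and may appear as intercurrent conditions.
- **About 87% of cases go unrecorded.** The 86.7% is calendar time outside the AE windows; pIMD collection runs through all of it.
- **Half the primary-endpoint events would be missing.** No diagnostic delay is given, and the endpoint counts diagnoses, which the AE window does not govern.

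The number affected cannot be estimated from the documents. At an assumed 1% incidence it would be some fraction of 0.7 expected cases in the vaccine group. This is a cheap improvement, not a threat to the study's conclusions.

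**What to change.** Reconcile 9.1.5, 9.3.1, Table 21, 9.5.1 and Tables 7 and 8 on one rule for suspected cases:

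1. In 9.3.1 and Table 21, add a category, *AE under evaluation as a possible pIMD* (a Table 20 disease or one the investigator suspects is autoimmune). Record it with causality from first vaccination to study conclusion.
2. In 9.5.1.1 and 9.5.1.2, follow these AEs as diagnosed pIMDs are followed, until the diagnosis is confirmed or excluded.
3. In Tables 7 and 8, state which AEs are to be recorded after the 30-day windows.
4. In Protocol 11.8 and the SAP safety section, list suspected and unresolved cases by group beside the confirmed pIMDs.

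The cost is protocol and SAP wording and a small number of extra AE records. Some non-specific symptoms will be followed that prove not to be pIMDs. The visits and the AE entries in the eCRF already exist, and no treatment changes.

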9.4.2. Reporting of pIMDs to GSK Biologicals

Once onset of a new pIMD or exacerbation of a pre-existing pIMD is diagnosed (serious or non-serious) in a study subject, the investigator (or designate) must complete the information in the electronic SAE report **WITHIN 24 HOURS** after he/she becomes aware of the diagnosis. A field on the SAE report allows specifying that the event is a pIMD and whether it is serious or non-serious. The SAE report will always be completed as thoroughly as possible with all available details of the event, in accordance with the pIMD standard questionnaire provided. Even if the investigator does not have all information regarding a pIMD, the report should still be completed within 24 hours. Once additional relevant information is received, the report should be updated **WITHIN 24 HOURS**.

The investigator will always provide an assessment of causality at the time of the initial report.

Refer to Section 9.4.3.1 for back-up system in case the electronic SAE reporting system does not work.

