11. STATISTICAL METHODS

11.1. Primary endpoints

- Occurrence of each solicited local adverse event (AE), during the 7-day follow-up period (*i.e.* day 0 - 6) following each vaccination, in all subjects.
- Occurrence of each solicited general AE, during the 7-day follow-up period (*i.e.* day 0 - 6) following each vaccination, in all subjects.
- Occurrence of any unsolicited AE, during the 30-day follow-up period (*i.e.* day 0 - 29) following each vaccination, in all subjects.

- Occurrence of each haematological/ biochemical laboratory abnormality at Day 0, Day 7, Day 30, Day 60, Day 67, Day 90, Day 270 and Day 450, in all subjects.
- Occurrence of any potential immune-mediated disease (pIMD) from first vaccination up to study conclusion, in all subjects.
- Occurrence of any serious adverse event (SAE) from first vaccination up to study conclusion, in all subjects.

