11.8. Analysis of safety

The analysis will be performed on the TVC. If the percentage of vaccinated subjects excluded from the ATP cohort for efficacy is at least 10%, a second analysis will be performed on the ATP cohort for efficacy to complement the first analysis.

The percentage of subjects with at least one **local AE** (solicited and unsolicited), with at least one **general AE** (solicited and unsolicited) and with any AE during the 7-day (day 0 – day 6) or the 30-day (day 0 – day 29) follow-up period will be tabulated after each vaccination and overall with exact 95% confidence interval (CI). The same computations will be done for Grade 3 AEs, for related AEs and for Grade 3 related AEs.

The percentage of subjects/doses reporting each individual solicited local (any grade, Grade 3) and general (any grade, Grade 3, related, Grade 3 related) AE during the 7-day (day 0 to day 6) follow-up period will be tabulated for each group as follows:

- Overall, the percentage of subjects with the symptom and its exact 95% CI.
- Overall, the percentage of doses with the symptom and its exact 95% CI.
- Per study vaccine dose, the percentage of subjects with the symptom and its exact 95% CI.

The exact 95% CIs will be calculated assuming independence between doses. For fever, additional analyses will be performed by 0.5°C increments.

The verbatim reports of **unsolicited** symptoms will be reviewed by a physician and the signs and symptoms will be coded according to the MedDRA Dictionary for Adverse Reaction Terminology. Every verbatim term will be matched with the appropriate preferred term (PT). The percentage of subjects with unsolicited symptoms during the 30-day follow-up period after any study vaccine dose with its exact 95% CI will be tabulated by group and by MedDRA PT. Similar tabulation will be done for the percentage of doses, for Grade 3 unsolicited symptoms, for unsolicited symptoms that resulted in a medically attended visit, for Grade 3 and causally related unsolicited symptoms and for unsolicited symptoms causally related to vaccination.

For each group and for each **haematology/ biochemistry parameter**:

- The percentage of subjects having results below or above the local laboratory normal ranges will be tabulated by time point.
- The maximum grading from Screening up to study conclusion will be tabulated. Grades will be based on the FDA Guidance for Industry “Toxicity Grading Scale for

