Healthy Adults and Adolescent Volunteers Enrolled in Preventive Vaccine Clinical Trials" (see **APPENDIX C**).

The number of subjects who experienced any **pIMD** or any **SAE** from first vaccination up to 6 months post-Dose 2 will be reported.

The number of subjects who experienced any **AE leading to study withdrawal**, from first vaccination up to study conclusion, or any **SAE related to study participation of concurrent GSK medication/ vaccination**, during the entire study period, will be reported.

Pregnancy exposures from first vaccination up to 6 months after last vaccination and pregnancy outcomes will be described in detail.

The percentage of subjects/ dose using **concomitant medication/ product** (any medication/ product, any antipyretic and any antipyretic taken prophylactically, respectively) during the 7-day follow-up period (day 0 – day 6) and during the 30-day follow-up period (day 0 – day 29) will be summarised per group for each dose and overall per dose.

11.8.1. iSRC safety evaluations

Unblinded review of safety data will be done during iSRC evaluations (refer to Section **9.10** for more information). No individual clinical study report will be written as a result of these safety evaluations.

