6.1.1. Analysis of safety

The analysis will be performed on the TVC. If the percentage of vaccinated subjects excluded from the ATP cohort for efficacy is at least 10%, a second analysis will be performed on the ATP cohort for efficacy to complement the first analysis.

The percentage of subjects with at least one **local AE** (solicited and unsolicited), with at least one **general AE** (solicited and unsolicited) and with any AE during the 7-day (day 0 – day 6) or the 30-day (day 0 – day 29) follow-up period will be tabulated after each

Statistical Analysis Plan

Study alias & e-track number(s): NTHi-004 (200157)

vaccination and overall with exact 95% confidence interval (CI). The same computations will be done for Grade 3 AEs, for related AEs and for Grade 3 related AEs.

The percentage of subjects/doses reporting each individual solicited local (any grade, Grade 3) and general (any grade, Grade 3, related, Grade 3 related) AE during the 7-day (day 0 to day 6) follow-up period will be tabulated for each group as follows:

- Overall, the percentage of subjects with the symptom and its exact 95% CI.
- Overall, the percentage of doses with the symptom and its exact 95% CI.
- Per study vaccine dose, the percentage of subjects with the symptom and its exact 95% CI.

The exact 95% CIs will be calculated assuming independence between doses. For fever, additional analyses will be performed by 0.5°C increments.

As during the study, some subjects have completed wrong diary cards (paediatric ones instead of adults), a sensitivity analysis will be done on subjects that have completed the correct diary cards to be sure that they were no impact on results.

The verbatim reports of **unsolicited** symptoms will be reviewed by a physician and the signs and symptoms will be coded according to the MedDRA Dictionary for Adverse Reaction Terminology. Every verbatim term will be matched with the appropriate preferred term (PT). The percentage of subjects with unsolicited symptoms during the 30-day follow-up period after any study vaccine dose with its exact 95% CI will be tabulated by group and by MedDRA PT. Similar tabulation will be done for the percentage of doses, for Grade 3 unsolicited symptoms, for unsolicited symptoms that resulted in a medically attended visit, for Grade 3 and causally related unsolicited symptoms and for unsolicited symptoms causally related to vaccination.

For each group and for each **haematology/ biochemistry parameter**:

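### Neither the protocol nor the SAP states a check of coded events against the sponsor's pIMD term list, so a listed diagnosis first entered as an ordinary AE can stay outside the pIMD count

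*Protocol*

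**What the plan says.** Protocol 11.1 lists as a primary endpoint "Occurrence of any potential immune-mediated disease (pIMD) from first vaccination up to study conclusion, in all subjects". Section 1.3.1 has one row in its risk table: vaccine-induced autoimmune disease, to be mitigated by close monitoring of pIMDs.

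Protocol 9.1.5 sets how a case acquires pIMD status. For the Table 20 diagnoses, "When there is enough evidence to make any of the above diagnoses, the AE must be reported as a pIMD". For diseases not on that list, "the investigator will exercise his/her medical and scientific judgement in deciding whether other diseases have an autoimmune origin". Findings that might represent a listed diagnosis are to be entered as AEs, and not as pIMDs, until the diagnosis is definitive. As aids, sites receive a standard questionnaire, and "a list of preferred terms (PTs) and PT codes corresponding to the above diagnoses will be available to investigators at study start". Section 9.4.2 gives the reporting route, which also covers non-serious cases: "A field on the SAE report allows specifying that the event is a pIMD and whether it is serious or non-serious".

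On the analysis side, Protocol 11.8 and SAP 6.1.1 (Amendment 1) have unsolicited verbatim terms reviewed by a physician and coded to a MedDRA preferred term. The percentage of subjects with each term in the 30-day periods after vaccination "will be tabulated by group and by MedDRA PT". For pIMDs there is one sentence: the number of subjects with any pIMD or SAE "from first vaccination up to 6 months post-Dose 2 will be reported". Neither document derives pIMD status in the dataset, uses the term list on coded data, or describes a reconciliation.

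**The concern.** The endpoint tied to the trial's one named risk depends on a label set at the site. The sponsor holds term codes for exactly the listed diagnoses and codes the unsolicited events, yet no step is stated that puts the two together.

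The plan's own rules leave a route by which a listed diagnosis can be recorded but not counted. A suspected case starts as an AE, so correct reporting needs a later reclassification. Protocol 9.5.1.1 has unresolved AEs reviewed at later contacts only until 30 days after the last vaccination; pIMDs and SAEs carry no such limit. A second place where a listed diagnosis can sit is the record of medically attended intercurrent conditions, kept to study conclusion (Protocol 7.7 and 9.3.1), with no stated link to the pIMD count.

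With few cases expected, one omission can decide whether a group shows a case at all.

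**Working it through.** **Inputs from the documents.** n = 70 in the vaccine group (Protocol 11.4), with 1:1 allocation (6.2.2.2.1). Unsolicited AEs are collected on days 0-29 after each of two doses (9.3.1). The final visit is Day 450. Six months post-Dose 2 is Day 240 (footnote e to Table 8).

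**Assumed.** The documents give neither the pIMD incidence p over the study nor the probability s that a true case is reported as a pIMD. Both are shown as ranges.

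**1. The plan's own figures.** The chance of at least one case is 1 - (1 - p)^70.
- p = 1%: 1 - 0.99^70 = 50.5% (Protocol 11.4 says more than 50%).
- p = 5%: 1 - 0.95^70 = 97.2% (the protocol says more than 97%).

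Both reproduce. They assume that every case is counted.

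**2. How often one case is the whole count.** P(exactly 1) = 70 × p × (1 - p)^69, divided by P(at least 1):

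| p | Expected cases | P(exactly 1) | P(at least 1) | Only case, given any |
|---|---|---|---|---|
| 0.5% | 0.35 | 24.8% | 29.6% | 84% |
| 1% | 0.70 | 35.0% | 50.5% | 69% |
| 2% | 1.40 | 34.7% | 75.7% | 46% |
| 5% | 3.50 | 10.2% | 97.2% | 10% |

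**3. Effect of incomplete reporting.** The chance of at least one counted case is 1 - (1 - p × s)^70:

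| p | s = 1 | s = 0.9 | s = 0.8 | s = 0.7 | s = 0.5 |
|---|---|---|---|---|---|
| 1% | 50.5% | 46.9% | 43.0% | 38.8% | 29.6% |
| 2% | 75.7% | 72.0% | 67.7% | 62.7% | 50.5% |
| 5% | 97.2% | 96.0% | 94.3% | 91.7% | 83.0% |

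The gap from the s = 1 column is an upper bound on what a term search could recover, because the search reaches only events that were recorded and coded.

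**4. What one case means.** 1/70 = 1.4% (exact 95% CI 0.04 to 7.7%); 0/70 = 0% (0 to 5.1%). Fisher's exact test gives p = 1.00 for 1/70 against 0/70, 0.058 for 5 against 0 and 0.028 for 6 against 0. The plan specifies no such test; the figures show only that one case does not separate the groups.

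**5. Reach of the search.** The two AE windows cover 2 × 30 = 60 of about 450 days, or 13%. Outside them, the recorded sources besides reported pIMDs are mainly SAEs and intercurrent conditions. The documents do not say that intercurrent conditions are MedDRA-coded.

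**6. The reporting window.** The endpoint (Protocol 11.1, SAP 4.1) runs to study conclusion, and the final analysis (Protocol 11.14.1, SAP 8.1) covers pIMDs to Day 450. The analysis text (Protocol 11.8, SAP 6.1.1) stops at 6 months post-Dose 2. That leaves 450 - 240 = 210 days in which even a correctly reported pIMD falls outside the stated count.

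**The case against.** The reporting duty is strong. Table 20 diagnoses must be reported once there is enough evidence, within 24 hours of the investigator learning of the diagnosis and whether or not serious, and sites have the table, the questionnaire and the term list. Investigator-confirmed diagnosis is a legitimate case definition. All of this stands. It is an instruction to sites, however, and no check that it was followed is stated.

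A reader might infer that the sponsor counts only flagged events and does not apply its list. The documents do not support that. They are silent on how the count is derived, and the SAP refers to a separate annex of tables and listings that is not among them. What can be said is that no rule is stated.

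A reader might also infer that one missed report wipes out the safety signal. It does not. An unreported case starting within 30 days of a dose still appears by group and preferred term, and a serious one still counts in the SAE endpoint. The SRT monitors safety on an ongoing basis and the iSRC reviews unblinded data. The planned iSRC evaluations are tied to the start of Dose 1 in GOLD 3 subjects and of Dose 2, though, and neither body is given the task of correcting the endpoint.

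A third temptation is to put a size on the benefit. Assume 0.5-2% incidence per year and 60-90% reporting. With λ = 70 × rate × 450/365 (0.43 to 1.73), exp(-sλ) - exp(-λ) gives a 3-18% chance that a case occurs in a group and none is counted. The arithmetic is right, but both inputs are assumed and the figure includes cases that were never recorded as coded events. It does not measure what a search would recover.

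Finally, adding every term match to the endpoint would conflict with the definitive-diagnosis rule in Protocol 9.1.5. That objection is sound and shapes the fix.

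**Conclusion.** The point holds as a modest, inexpensive improvement. The pIMD endpoint rests on investigator reporting, and neither document states a reconciliation of coded events against the existing term list. The rules on suspected cases and AE follow-up make it possible for a listed diagnosis to be recorded and yet stay outside the count. At an assumed 1% incidence, 0.7 cases are expected per group and any case that occurs is the only one 69% of the time, so one omission can turn a count of 1 into 0. The loss is a case from the pIMD count; it need not vanish from the safety data, and it does not change a between-group conclusion. How often this would happen cannot be derived from the documents. The window mismatch in step 6 needs no assumption and can exclude correctly reported cases.

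**What to change.** In SAP 6.1.1:

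- Keep investigator-confirmed pIMDs as the endpoint.
- Add a programmed search of coded unsolicited AEs and SAEs against the existing term list, from first vaccination to study conclusion. Include intercurrent medical conditions if they are coded.
- Have it run by someone without access to treatment assignments. This needs saying because the project statistician is unblinded at the Day 90 analysis (Protocol 6.3 and 11.14.1).
- Query unflagged matches with the site. Count those the site confirms, and show the rest as a separate supplementary count by group.
- State that the search reaches only recorded and coded events, so its yield outside the 30-day windows is limited.

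In the same edit, reconcile the 6-month cut-off in Protocol 11.8 and SAP 6.1.1 with the study-conclusion endpoint and the Day 450 analysis.

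The cost is a short program using a list that already exists and a few site queries, plus coding work if intercurrent conditions are to be included and are not yet coded. A broad term may pull in a non-autoimmune event; the site query and the separate count deal with that.
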